2 OBJECTIVES

Aim 1: Randomize IBS-D subjects to receive either treatment with a nonabsorbable antibiotic rifaximin vs. low FODMAP dietary intervention.

- a) 200 IBS-D patients will be carefully phenotyped using validated questionnaires (IBS symptoms, stool form, psychological function, quality of life) and diet analysis.
- b) IBS-D subjects will undergo baseline testing including glucose hydrogen breath tests (GHBT) to define the presence of SIBO. Fecal microbiota will also be characterized by α - and β -diversity and dominant phyla on 16S RNA analyses.
- c) IBS-D subjects will be randomized to receive either rifaximin 550 mg three times daily $\times 14$ days or low FODMAP diet $\times 4$ weeks under direction of study bionutritionist.
- d) The primary outcome will be changes in mean daily pain or bloating by visual analog scale (VAS) after intervention compared with baseline. Responders to intervention will be defined by $\geq 30\%$ reductions in mean daily pain or bloating by VAS compared with baseline. Secondary outcomes will be defined by reduction in IBS Symptom Severity Scale by ≥ 50 compared with baseline.
- e) Other secondary outcomes, including GI symptoms, stool form, psychological function, quality of life, and diet intake, will be compared to determine if subjects present differently.

Aim 2: Determine using longitudinal analyses how SIBO status and fecal microbiota features associate with response to treatment with rifaximin or a low FODMAP dietary intervention.

- a) Fecal microbial analyses will be repeated at 2, 4 and 5 weeks while GHBT will be repeated at the end of the intervention.

- b) The primary aim will be change in fecal microbial diversity after intervention compared with baseline. We hypothesize that low FODMAP diet will result in a 10-15% increase in diversity in fecal microbiota compared with baseline.
- c) Secondary outcomes including response to treatment with rifaximin or low FODMAP diet will be related to the (i) presence of SIBO on initial testing, (ii) persistence of SIBO after intervention, (iii) abnormal α - and β -diversity on initial testing, (iv) changes in α - and β -diversity as well as in dominant microbial phyla at 2, 4 and 5 weeks, and (v) changes in serum cytokine profiles, including TNF- α , IL-1 β , IL-6, IL-8, and IL-10.

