Trial Protocol: In order to minimize unequal allocation between arms, IBS-D subjects will be randomized using block randomization with random permuted sizes of 2 or 4 in a 1:1 ratio into two arms: one group will undergo treatment with rifaximin 550 mg three times daily for 14 days. The second group will be placed on a low FODMAP diet (≤ 9 grams per day as previously described) for 4 weeks (40,64,65). IBS-D subjects undergoing dietary intervention will undergo consultation with a bionutritionist knowledgeable in low FODMAP diets. A diet plan will be implemented and individualized to subjects based on information from their dietary history. Written information regarding allowable vs. non-allowable food items will be provided to IBS-D subjects and bionutritionists will be available during the study for further education. IBS-D subjects randomized to the low FODMAP diet group will meet with the GI nutritionist at the completion of the 2nd week of dietary intervention to answer any potential questions regarding the diet. IBS-D subjects will complete a 24-hour dietary recall each week or every two weeks during the 4-week dietary intervention to ensure compliance.

Symptom Assessment: IBS-D subjects will record stool frequency, BSFS, and symptom scores for abdominal pain and bloating daily on a diary card. IBS-D subjects will complete questionnaires on a weekly basis during study visits to determine changes in symptoms. Responders to intervention arm (both rifaximin and low FODMAP diet) will be defined as $\geq 30\%$ reductions in mean daily pain or bloating compared with baseline. Secondary outcomes, including reduction in IBS Symptom Severity Scale by ≥ 50 compared with baseline at the end of the interventional arm, will also be monitored. These are both considered to reflect clinically meaningful improvements in IBS (55,57). IBS-D subjects will be seen on a weekly or biweekly basis and diary cards will be collected. Adherence to medications or dietary intervention will also be assessed at that time.

Specific Aim 2: Determine using longitudinal analyses how SIBO status and fecal microbiota-derived metrics associate with response to treatment with rifaximin or a low FODMAP dietary intervention.

2A. Research Approach:

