We will prospectively follow the results of GHBT and fecal microbiota before and after treatment with rifaximin and low FODMAP dietary restriction. We will collect fecal samples throughout the study period in IBS-D patients. All IBS-D subjects will also undergo GHBT before and after

intervention. The primary aim will be change in fecal microbial diversity after intervention with rifaximin or low FODMAP diet compared with baseline. Secondary outcomes will evaluate whether response to treatment with rifaximin or low FODMAP diet is associated with: (i) presence of SIBO on initial testing, (ii) persistence of SIBO after intervention, (iii) changes in α - and β - diversity as well as in dominant phyla. We will also utilize human intestinal enteroids to model how host-microbial interactions may influence response to treatment with rifaximin or low FODMAP diet in IBS.

2B. Experimental Methods:

Fecal Collection and Preparation: Stool samples will be collected from all IBS-D subjects at weeks 2, 4 and 5 as described in Aim 1. Stool samples will be stored for up to 5 years at the conclusion of the study for future analyses, including evaluating differences in metabolomics, such as histamine, p-hydroxybenzoic acid, azelaic acid, and H₂ (45). This portion of the study is optional, and subjects have a choice to allow their stool samples to be stored for this sub-study. This may provide mechanistic descriptions of how changes in gut microbiota lead to changes seen in IBS. If patients consent to this optional portion of the study, they will provide a stool sample in 95% ethanol at weeks 0, 2, 4, and 5. Subjects will be compensated a nominal amount of \$20 for stool samples returned at week 0 and \$10 each for weeks 2, 4 and 5 to express our gratitude for their participation in the study. We will also provide mailers to mail back samples to minimize study burden on participants.

GHBT: Glucose H₂/CH₄ test will be repeated at week 5 as described in Aim 1.

Serum cytokine profiles: Serum cytokines will be repeated at week 5 as described in Aim 1. Handling and processing of the blood will be described in Appendix 1.

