We will develop and validate a predictive model of response to low FODMAP diet using data from the subjects randomized to a low FODMAP diet (Aim 1) combined with existing data from a separate cohort of IBS-D subjects previously treated with a low FODMAP diet (HUM 00053274).

3B. Experimental Methods:

We will use the combined cohort of patients treated with a low FODMAP diet (Aim 1 and HUM #00053274), which will be split into a training set from a random sample of 80% of the data while the remaining 20% of the data will serve as the test set. Using a random forest model, 5x2 nested cross-validation (CV) will be performed within the training set for model selection and hyperparameter tuning. The candidate models will be compared by testing for overlap of confidence intervals for area under the curves (AUCs, two-sided test). Once a final model is selected, model performance will be evaluated on the test set.

Study Timeline:

Figure 1 IBS Subject Timeline

Schedule of Events - Low FODMAP Group

Visit Number	Pre-Visit	Visit 1	Visit 2	Visit 3	Visit 4	Visit 5
Visit Description	Pre-screening (Phone/in person)	Baseline (Phone/in person)	Monitoring (Phone/in person)	Monitoring (Phone/in person)	Monitoring (Phone/in person)	Monitoring/Outcomes (Phone/in person)
Time point	Eligibility	Day 0	Day 7±3 days	Day 14±3 days	Day 28±3 days	Day 35±3 days
7 day pre-screening questionnaire	X					
Informed Consent	X					
Medical History /Physical Examination		X	X	X	X	X
Urine pregnancy test (Females of childbearing age)		X				
Washout	X					
Questionnaires		X		X		X

3-day food diary		X				
24-hour dietary recall			X	X	X	X
GI nutrition consultation		X		X		
Colonoscopy with mucosal biopsies (optional)	X					
Serum Cytokine Profiles (optional)		X				X
Buccal swab collection (optional)		X				
Glucose hydrogen breath testing		X				X
Stool collection for fecal microbial analysis		X (3 baseline samples)		X	X	X
Randomization	X					
Dietary Compliance			X	X	X	X
Adverse Events Monitoring			X	X	X	X

*Female participants capable of bearing children will be required to attend visit 1 in person for the pregnancy test

*During COVID-19 pandemic, all hydrogen breath tests will be conducted remotely

Schedule of Events – Rifaximin Group

*Female participants capable of bearing children will be required to attend visit 1 in person for the pregnancy test

*During COVID-19 pandemic, all hydrogen breath tests will be conducted remotely

Visit Number	Pre-Visit	Visit 1	Visit 2	Visit 3	Visit 4	Visit 5

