Visit Description	Pre-screening (Phone/in person)	Baseline (Phone/in person)	Monitoring (Phone/in person)	Monitoring (Phone/in person)	Monitoring (Phone/in person)	Monitoring/Outcomes (Phone/in person)
Time point	Eligibility	Day 0	Day 7±3 days	Day 14±3 days	Day 28±3 days	Day 35±3 days
7 day pre-screening questionnaire	X					
Informed Consent	X					
Medical History /Physical Examination		X	X	X	X	X
Urine Pregnancy Test (Females of childbearing age)		X				
Washout	X					
Questionnaires		X		X		X
3-day food diary		X				
24-hour diet recall			X	X	X	X
Colonoscopy with mucosal biopsies (optional)	X					
Serum cytokine profiles (optional)		X				X
Buccal swab collection (optional)		X				
Glucose hydrogen breath testing		X				X
Stool collection for fecal microbial analysis		X (3 baseline samples)		X	X	X
Randomization	X					
Medication Dispensing		X				
Medication Compliance			X	X		
Adverse Events Monitoring			X	X	X	X

7 Data Collection and Management Procedures

Data Handling and Entry: All data including questionnaire results and physiologic testing will be recorded and reviewed by the study team. Data will then be entered into an electronic case report form (eCRF) that complies with Title 21 of the Code of Federal Regulations (21 CFR Part 11). All passwords will be strictly confidential to protect subject's protected health information (PHI). Only the Primary Investigator (PI) and Study Coordinator will have access to the data and subject identifiers. Only the PI and Study Coordinator will be allowed to enter data onto the password-protected web-based server.

Computer Systems: Data entry will be entered into REDCAP which is validated and conforms to regulatory requirements. Only the Primary Investigator (PI) and Study Coordinator will have access to the data and subject identifiers. Only the PI and Study Coordinator will be allowed to enter data onto the password-protected web-based server.

Phone Visits: All phone visits will be conducted with a University Health System phone to protect patient confidentiality.

SignNow: a secure application that enables users to electronically prepare and send University business documents for the purpose of requesting and obtaining digital signatures to help protect confidentiality.

Data Validation: Validation checks will be programmed within the eCRF system as well as supplemental validation performed by review of the downloaded data, will be applied to the data in order to ensure accurate, consistent, and reliable data.

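### As scheduled, the 4-week diet arm has no end-of-diet IBS-SSS, and the stool that marks the end of intervention for the Aim 2 primary change is not named and could be a post-diet one

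*Combined protocol and SAP*

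**What the plan says.** **Duration.** Section 2 (Aim 1 c) and section 6 (1B, Trial Protocol) both give the low FODMAP diet 4 weeks. The latter adds: "IBS-D subjects will complete a 24-hour dietary recall each week or every two weeks during the 4-week dietary intervention to ensure compliance". No start or stop day is stated in the available text. Patients in this arm "will meet with the GI nutritionist at the completion of the 2nd week of dietary intervention", and the Schedule of Events marks nutrition consultations at Visit 1 (Day 0) and Visit 3 (Day 14±3).

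**Compliance rows.** In the Low FODMAP schedule the row "Dietary Compliance" is marked at Visits 2 to 5, so through Day 35±3. In the Rifaximin schedule the row "Medication Compliance" stops at Visit 3, when 14 days of dosing end.

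**Symptom questionnaires.** Section 6 (1B, Symptom Assessment) defines the secondary response as an IBS-SSS reduction of at least 50 "compared with baseline at the end of the interventional arm". It also says: "IBS-D subjects will complete questionnaires on a weekly basis during study visits". Section 3 likewise describes surveys at every visit. Both schedules mark Questionnaires only at Visits 1, 3 and 5.

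**Breath test.** Section 2 (Aim 2 a) says "GHBT will be repeated at the end of the intervention". Section 6 (2B, GHBT) says that the "test will be repeated at week 5 as described in Aim 1". Section 6 (2A) speaks more loosely of testing before and after intervention.

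**Stool.** Samples are taken at baseline and at weeks 2, 4 and 5. Section 10 (Aim 2) powers the primary change in diversity at the end of the intervention, without saying whether that is the week 4 or the week 5 sample.

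**The concern.** If the diet stops after the stated 4 weeks, Visit 5 comes after it. The IBS-SSS response is defined at the end of the intervention, but the schedule collects the questionnaire at mid-diet (Visit 3) and then only at Visit 5. A site that follows the schedule would have no value at the time the outcome names.

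The Aim 2 primary change has a related weakness. A week 4 stool exists, but nothing stops an analyst from taking the last sample, at week 5, as the end of the intervention. In the diet arm that sample could reflect a week of unrestricted eating. Section 1 itself says that diet strongly shapes the composition of the gut microbiota, so the choice of sample matters and should be fixed in advance.

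The available text does not say what diet-arm patients should eat between the end of week 4 and Visit 5, apart from the low-carbohydrate preparation for the breath test (section 3, General risks). Staff could therefore instruct patients differently, and no diet stop date is listed for recording.

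**Working it through.** The plan gives no figure to reproduce. The check is calendar arithmetic on the visit schedule.

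**Inputs**
- Diet length: 28 days (sections 2 and 6).
- Visit 3 window: Day 11 to 17. Visit 4: Day 25 to 31. Visit 5: Day 32 to 38 (Schedule of Events).
- Second consultation at the end of diet week 2, held at Visit 3.

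**Step 1. Range of start days.** Let S be the diet start day. The first consultation is on Day 0, so S ≥ 0. Diet week 2 ends on S + 14, which must lie in the Visit 3 window: S + 14 ≤ 17, so S ≤ 3. A start slightly after Day 0 is plausible, because section 10 has three stools collected before treatment.

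**Step 2. Diet end and gap to later visits.** Diet end = S + 28. Gap to Visit 5 = (32 to 38) − (S + 28).

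| Start day S | Diet end | Days from diet end to Visit 5 | Visit 4 window days after diet end |
|---|---|---|---|
| 0 | Day 28 | 4 to 10 | 3 of 7 (Days 29–31) |
| 1 | Day 29 | 3 to 9 | 2 of 7 |
| 2 | Day 30 | 2 to 8 | 1 of 7 |
| 3 | Day 31 | 1 to 7 | 0 of 7 |

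All 4 × 7 = 28 combinations of start day and Visit 5 day fall after a 4-week diet.

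**Step 3. Could a later start remove the gap?** For a 4-week diet to end on Day 35, S must be 7. Diet week 2 would then end on Day 21, outside the Visit 3 window, and a nominal Day 7 compliance check would cover no diet days. Even S = 4 (diet end Day 32) puts the end of week 2 on Day 18, one day outside the window.

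**Step 4. What if the diet runs to Visit 5?** It would last 32 to 38 days with S = 0 and 29 to 35 days with S = 3, so 4.1 to 5.4 weeks.

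**Step 5. Which measures are involved (diet arm)**

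| Measure | Post-baseline times in the schedule | Timing given in the text | Week 4 value scheduled? |
|---|---|---|---|
| IBS-SSS | Visits 3, 5 | End of the interventional arm | No |
| Stool, Aim 2 primary change | Visits 3, 4, 5 | End of the intervention, visit not named | Yes |
| Breath test | Visit 5 only | End of the intervention; week 5; after intervention | No |
| Cytokines (optional) | Visit 5 only | Week 5 | No |

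**Step 6. The same calendar for rifaximin.** With dosing from Day 0, treatment ends on Day 14. The week 5 breath test is then 35 − 14 = 21 days later (18 to 24 over the Visit 5 window).

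**The case against.** The best defence is that week 5 is a common post-treatment assessment. The sentence in section 2 that puts the breath test at the end of the intervention covers both arms, and for rifaximin the week 5 test comes 18 to 24 days after dosing. The phrase therefore cannot mean on treatment throughout the trial. Section 6 (2A) says after intervention. This stands: a post-treatment breath test at week 5 is a legitimate choice, and only the wording in section 2 needs tidying.

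A reader might also infer from the Day 35 compliance mark that the diet really lasts 5 weeks, and so that either the stated duration is wrong or every week 5 measure is off diet. The documents do not go that far. If Visit 4 falls on Day 25, 3 diet days remain with a Day 0 start and 6 with a Day 3 start, and only Visit 5 can check them. The contrast with the rifaximin compliance row is suggestive, no more. The 24-hour recall at Visit 5 proves nothing, since both arms have it. No passage tells patients to stop or to reintroduce foods at Day 28, so what they eat in week 5 is unstated rather than known to be off diet. Figure 1, the subject timeline, is not available and may give a stop day.

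It can be said, too, that the text already promises questionnaires at each visit or weekly, that Aim 2 is called exploratory with intermediate time points to be examined, and that cytokines are optional. These limit the impact. They do not settle which of text and schedule the sites will follow for the IBS-SSS, or which stool carries the Aim 2 primary change.

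**Conclusion.** The point holds in a limited form. Followed as written, a 4-week diet ends about Day 28 to 31 and Visit 5 falls 1 to 10 days later. The schedule then supplies no end-of-diet IBS-SSS for an outcome defined at the end of the intervention, and it leaves open whether the Aim 2 primary change uses the week 4 stool or a week 5 stool taken after the diet. Both should be corrected.

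This rests on two assumptions: that the diet starts on Day 0 to 3, inferred from the two consultations, and that patients stop at 4 weeks as stated. If they continue to Visit 5, the week 5 measures are on diet and the stated duration is what needs correcting.

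The size and direction of any bias cannot be derived from the documents. The week 2 stool and most or all week 4 stools are on diet, so a suitable end-of-diet sample exists once it is named. The Aim 1 daily pain and bloating outcome is not affected by this point. Nor do the documents require a 5-week diet: that would change the intervention, and it would make the week 5 comparison less symmetrical, with diet measured on treatment and rifaximin about three weeks after it.

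**What to change.** Keep the 4-week diet, and:

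1. Mark Questionnaires at Visit 4 in both arms, and use the Visit 4 IBS-SSS as the diet arm's end-of-intervention value.
2. Name the Visit 4 stool, collected while patients are still on the diet, as the diet arm's end-of-intervention sample for the Aim 2 primary change.
3. Reword section 2 (Aim 2 a) so that the breath test is at week 5, after intervention.
4. Treat the diet arm's Visit 5 measures as post-diet follow-up.
5. Record each patient's diet start and stop dates.

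The cost is one extra questionnaire set at an existing visit, which sections 3 and 6 already imply, and up to 31 − 28 = 3 more days of diet if Visit 4 is late. The rest is protocol wording, schedule marks and two recorded dates. No visit or sample is added.

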3 EXPECTED RISKS/BENEFITS

The data accumulated in this study will advance our understanding of the pathophysiology of IBS, including the role of the gut microbiota and SIBO in the pathogenesis of IBS, and may provide important information on which IBS subjects will most benefit from therapies including dietary modification and rifaximin.

There are potential direct benefits for all IBS subjects in this study. On study entry, glucose hydrogen breath tests (GHBT) as well as analysis of fecal microbiota will be performed that may provide new insight into causes of symptoms in patients with IBS. Furthermore, subjects with IBS will be treated with well accepted treatments for IBS, including a nonabsorbable antibiotic rifaximin or diets low in FODMAP. IBS-D subjects treated with low FODMAP diet will be provided education on a low FODMAP diet from a trained bionutritionist. IBS-D subjects will track their symptoms by completing questionnaires online including the Bristol Stool Form Scale as well as an 11-point NRS on abdominal pain and bloating daily. IBS-D subjects will be asked to complete these questionnaires after their evening meal. They will also be instructed to track their diet for 24 hours prior to each weekly or biweekly visit using a food questionnaire. Finally, all IBS-D subjects will be seen or receive a phone call by the PI and/or study team every week or every two weeks during the study. At each visit, survey information will be obtained using validated questionnaires including IBS-Symptom Severity Scale, Gastrointestinal Symptom Rating Scale-IBS, Patient Health Questionnaire (PHQ-9), Visceral Sensitivity Index (VSI), and IBS-quality of life (IBS-QOL). The IBS-Symptom Severity Scale is a 10-item questionnaire that tracks severity of IBS symptoms and is a

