6 STUDY DESIGN AND PROCEDURES

Specific Aim 1: Randomize IBS-D subjects to receive either a nonabsorbable antibiotic rifaximin vs. low FODMAP dietary intervention.

1A. Research Approach:

200 IBS-D subjects will be carefully phenotyped using validated questionnaires (IBS symptoms, stool form, psychological function, quality of life) and diet analysis. IBS-D subjects will also undergo baseline testing including GHBT as well as fecal microbial analysis. IBS-D subjects will then be randomized to receive either rifaximin or low FODMAP diet intervention at the initial screening visit. Efficacy of therapies will be monitored with validated questionnaires to track symptomatic improvement. The primary outcome will be changes in mean daily pain or bloating after intervention compared with baseline. Responders to intervention will be defined as $\geq 30\%$ reduction in mean daily pain or bloating by visual analog scale (VAS) compared with baseline. Secondary outcomes will monitor changes in IBS-Symptom Severity Score as well as differences in GI symptoms, stool form, psychological function, quality of life, and dietary intake before and after intervention.

1B. Experimental Methods:

Subject Recruitment: 200 adult subjects ≥ 18 years of age who meet Rome IV criteria for IBS-D will be enrolled in the study. Women of childbearing age will undergo a urine pregnancy test to exclude the possibility of pregnancy. Women who are breastfeeding will also be excluded. IBS-D subjects will be excluded if they have underlying celiac disease, inflammatory bowel disease, or other organic disease that could explain their symptoms. All IBS-D subjects will have prior sigmoidoscopy or colonoscopy with mucosal biopsies within the past 2 years to rule out microscopic colitis. IBS-D subjects with a history of GI tract surgery, except for appendectomy, will also be excluded from the study. Antibiotics taken within 3 months prior to enrollment will not be permitted (54). IBS-D subjects on probiotics must discontinue their use at least 1 month prior to fecal collection. IBS medications, including anti-depressants, will be allowed if the dose has been stable for at least 1 month before inclusion. Medications will be carefully tracked to follow any potential confounding issues. IBS-D subjects who have previously received formal

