dietary education for IBS, including a low FODMAP diet, or previously received antibiotics, including rifaximin, for treatment of IBS-D or SIBO will be excluded from the study.

GI Symptom Assessment: All IBS-D subjects will complete validated questionnaires to quantify severity of IBS symptoms, including IBS Symptom Severity Scale (IBS-SSS), Gastrointestinal Symptom Rating Scale-IBS (GSRS-IBS), an 11-point numerical rating scale (NRS) for abdominal pain and bloating, and Bristol Stool Form Scale (BSFS) at baseline (55–58). The NRS for abdominal pain and bloating and the BSFS will be completed online through the REDCap Survey Tool.

Psychological and Quality of Life Assessment: IBS-D subjects will also complete validated questionnaires to assess for presence of and to measure severity of psychological disorders, GI specific anxiety, and impairments in quality of life. All IBS-D subjects will complete the Patient Health Questionnaire (PHQ-9), Visceral Sensitivity Index (VSI), and IBS-quality of life (IBS-QOL) (59–61). The PHQ-9 will be reviewed by the study team within 24 hours of completing the questionnaire. If a subject answers affirmative to the question “Thoughts that you would be better off dead or of hurting yourself in some way,” they will be provided with the appropriate referral to mental health counseling and/or the subject’s PCP will be alerted.

Dietary Assessment: All IBS-D subjects will undergo initial consultation with the study team and will be instructed on how to monitor and record their dietary intake. IBS-D subjects will then record daily their dietary intake for 3 days prior to fecal collection.

Fecal Collection and Preparation: Three fresh stool samples will be collected from all IBS-D subjects at baseline. Each sample will be immediately placed into an OMNIgene•GUT collection tube (DNA Genotek, Inc., Ottawa, ON, Canada) which allows for self-collection and stabilization of fecal DNA samples for up to 60 days at ambient temperature (62). Samples will then be mailed back or picked up by the study team and stored at -80°C in [name]’s Lab for long-term storage. If patients consent to the optional portion of the study, they will provide a stool sample in 95% ethanol at Visits 1, 3, 4, and 5. We will also collect a one-time stool sample and symptom questionnaires from healthy controls. Healthy controls will not have a history of gastrointestinal conditions and do not report any abnormal bowel movements or abdominal pain.

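### Both schedules measure diet by a 3-day diary before treatment and by 24-hour recall after it, so the within-arm change in dietary intake confounds instrument with time

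*Combined protocol and SAP*

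**What the plan says.** Section 6, Aim 1, 1A (Research Approach) lists among the secondary outcomes differences in "quality of life, and dietary intake before and after intervention". Section 2, Aim 1(e) also names diet intake as a secondary outcome. Section 10, Aim 1 makes the analysis paired within subject.

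Diet measurement is described in four places:

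- **Section 6, Aim 1, Dietary Assessment:** subjects "record daily their dietary intake for 3 days prior to fecal collection".
- **Section 6, Aim 1, Trial Protocol:** subjects "complete a 24-hour dietary recall each week or every two weeks during the 4-week dietary intervention to ensure compliance".
- **Section 3:** subjects are told to "track their diet for 24 hours prior to each weekly or biweekly visit using a food questionnaire".
- **Schedules of Events, both arms:** the row "3-day food diary" has one mark, at Visit 1 (Day 0). The recall row ("24-hour dietary recall" in the diet arm, "24-hour diet recall" in the rifaximin arm) is marked at Visits 2, 3, 4 and 5 (Days 7, 14, 28 and 35) and not at Visit 1.

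Section 6, Aim 2, 2B adds stool collections at weeks 2, 4 and 5 and refers back to Aim 1 for how they are done. No section gives a rule for calibrating the two instruments, or for averaging recalls, or says which visit counts as after intervention for diet.

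**The concern.** A before-after difference can be read as a change in diet only if intake is measured the same way both times. Here all baseline values come from a diary kept over three days, and all later values from a one-day recall. The two may differ systematically in what people report, and the paired analysis has no means of separating that difference from a real change.

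At stake are a stated secondary outcome and the evidence that the diet was delivered. Section 1 itself faults earlier microbiota studies for leaving diet out of account, so sound diet data matter to the trial's own argument. The text and the schedules can also be read differently, so staff could reasonably follow either.

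**Working it through.** The plan states no sample size, power or alpha for diet intake, so it has no figure of its own to reproduce on this point.

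**Step 1: which instrument is used when.** The pattern is the same in both arms.

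| Visit | 3-day diary | 24-hour recall | Stool |
|---|---|---|---|
| 1 (Day 0) | yes | no | yes |
| 2 (Day 7) | no | yes | no |
| 3 (Day 14) | no | yes | yes |
| 4 (Day 28) | no | yes | yes |
| 5 (Day 35) | no | yes | yes |

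No visit has both instruments and none spans baseline and follow-up. If a record is due before each stool collection, the diary column should also be marked at Visits 3, 4 and 5. It is not.

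**Step 2: what a pure instrument difference would do.** Assume no true diet change, a two-sided 5% paired t-test, and a diary-recall difference of b SDs of the change score. The probability of declaring a change is the power of the noncentral t with noncentrality b√n. Section 10 speaks of 32 per arm; 200 subjects split 1:1 gives 100.

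| b | n = 32 | n = 100 |
|---|---|---|
| 0.1 | 8.5% | 16.8% |
| 0.2 | 19.5% | 50.8% |
| 0.3 | 37.6% | 84.4% |
| 0.5 | 78.2% | 99.9% |

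The documents do not give b, so this is a range and not an estimate.

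**Step 3: noise in the change score under each design.** Assume independent days of equal variance, mean intake M, between-person CV c_b and day-to-day CV c_w. With k1 days before and k2 days after, and no diet change:

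SD of change = M × √(1 + c_b²) × c_w × √(1/k1 + 1/k2)

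M = 18 g/day and the CVs are assumptions. Scenario A has c_b = 0.3 and c_w = 0.5; scenario B has 0.4 and 0.6. For the present design in A: 18 × √1.09 × 0.5 × √(4/3) = 10.85 g.

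| Design | 1/k1 + 1/k2 | SD, A | SD, B |
|---|---|---|---|
| 3-day diary v one recall (now) | 1.33 | 10.85 g | 13.43 g |
| 3-day diary v 3-day diary | 0.67 | 7.67 g | 9.50 g |
| One recall v mean of three recalls | 1.33 | 10.85 g | 13.43 g |
| One recall v one recall | 2.00 | 13.29 g | 16.45 g |

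Every SD is proportional to M. At M = 12 g the present design gives 7.2 and 9.0 g; at M = 30 g, 18.1 and 22.4 g. The ratios between designs do not depend on M: one recall against one recall has √(2/1.33) = 1.22 times the present SD, and diary against diary √(0.67/1.33) = 0.71 times.

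**Step 4: putting b on the intake scale.** If day-to-day noise is the only source of spread, b = 0.3 is 0.3 × 10.85 = 3.3 g in A and 0.3 × 13.43 = 4.0 g in B. That is 18% and 22% of mean intake.

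**The case against.** The strongest reply has four parts.

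- **Follow-up is not one recall.** Each subject has four, and three of them (Visits 2 to 4) fall in the diet weeks if the diet starts at Visit 1. Averaging three matches the diary's number of days. This stands as regards noise. It does not remove a systematic difference between instruments, and the plan does not specify averaging.
- **The arms are treated alike.** A shift common to both arms cancels in a between-arm comparison of change. This stands, but Section 10 describes a within-subject analysis for Aim 1, where it does not cancel.
- **The text may already require repeat diaries.** Dietary Assessment, read with the later stool collections, allows this. Section 3 may even describe a one-day record and not a recall. This stands as a possible reading, but both schedules contradict repeat diaries, so the documents still need an edit.
- **The recall is there for compliance.** That is its stated purpose. It is also the only diet measure scheduled after baseline, so the before-after outcome has to use it.

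A reader might go further and infer that the switch from three days to one would by itself raise the share of subjects at or below 9 g/day, or lower the recorded median. The documents do not support making that the finding. The 9 g figure defines the diet, and no analysis of the share meeting it is planned. The mean, which a paired t-test compares, does not depend on the number of days. Any such shift also rests on an assumed mean intake, and it vanishes when three recalls are averaged (at 18 g/day, 6.6% v 6.6% in A and 13.4% v 13.5% in B). Nor do the documents list an analysis linking diet change to microbiota change.

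**Conclusion.** The point holds in a limited form. If the schedules are followed, instrument and time point are completely confounded, and the within-arm change in dietary intake cannot be read as change in diet alone. That rests on the schedules and needs no assumption. The size of the bias is unknown because the documents give no diary-recall difference. The rejection rates above show only that a modest difference could be mistaken for a diet change, given alpha of 0.05 and the stated values of b.

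The reach is narrow: one secondary outcome and the description of adherence. The symptom primary outcome is not affected, recalls at Visits 2 to 5 remain comparable with one another, and the between-arm difference in change is protected so far as the shift is common to both arms. It should be corrected, but it does not threaten the trial's main conclusion.

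**What to change.** Reconcile Section 3, the Dietary Assessment and Trial Protocol paragraphs of Section 6 (Aim 1), the stool collection paragraph of Aim 2 and both schedules, so that one instrument is used before and after treatment in both arms. There are two workable options:

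1. **Mark the 3-day diary at the outcome visits as well.** This matches instrument and number of days and has the lowest noise (7.67 and 9.50 g in the two scenarios). It costs three more days of recording per added visit. Subjects still in follow-up can benefit, since they already have a baseline diary.
2. **Add a 24-hour recall at Visit 1 and compare it with the mean of the recalls at Visits 2 to 4.** Noise stays about where it is now (10.85 and 13.43 g). It costs one short recall per subject and one schedule mark, but helps only subjects who have not yet passed Visit 1. Use the same visits in both arms, and note that Day 28 falls after the 14-day rifaximin course.

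Comparing one recall with one recall is not advised: it removes the instrument difference but raises the SD of change to 13.29 and 16.45 g.

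Under either option, state which visits define after intervention and how repeated measures are averaged. For subjects whose data cannot be matched, label the within-arm change as a comparison across instruments and rely on the between-arm difference in change.
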